5.4.3. Sensitivity Analyses

No sensitivity analyses planned.

5.4.4. Supplementary Analyses

No supplementary analyses planned.

5.4.5. Subgroup Analyses

No subgroup analyses are planned.

5.5. Safety Analyses

5.5.1. Extent of Exposure

As this is a single dose study, summaries of exposure will be limited to the number of participants exposed and the number of participants with interruptions or infusion stopped early and not completed. This will be presented with participant disposition.

5.5.2. Adverse Events

Adverse events analyses including the analysis of adverse events (AEs) and Serious AEs (SAEs) will be based on GSK Core Data Standards. All adverse events reported will be treatment emergent adverse events.

An overview summary of AEs, including counts and percentages of participants with

- any AE
- AEs related to study intervention
- AEs leading to permanent discontinuation of study intervention,
- study intervention related AEs leading to permanent discontinuation of study intervention,

- AEs leading to dose interruption,
- Common AEs, with common AE defined as any AE with an incidence of at least 5% in any of the treatment group
- SAEs,
- SAEs related to study intervention,
- fatal SAEs
- fatal SAEs related to study intervention

Adverse events will be coded using the standard Medical Dictionary for Regulatory Affairs (MedDRA dictionary).

A summary of number and percentage of participants with any adverse events by maximum intensity will be produced. AEs will be sorted by Preferred term (PT) in descending order. The summary will use the following algorithms for counting the participant:

- **Preferred term row:** Participants experiencing the same AE preferred term several times with different intensities will only be counted once with the maximum grade.
- **Any event row:** Each participant with at least one adverse event will be counted only once at the maximum intensity no matter how many events they have.

The frequency and percentage of AEs (all intensities) will be summarized and displayed in two ways: 1) in descending order by PT only and 2) in descending order by SOC and PT. In the SOC row, the number of participants with multiple events under the same SOC will be counted once.

A separate summary will be provided for study intervention-related AEs. A study intervention-related AE is defined as an AE for which the investigator classifies the possible relationship to study intervention as “Yes”. A worst-case scenario approach will be taken to handle missing relatedness data, *i.e.* the summary table will include events with the relationship to study intervention as ‘Yes’ or missing. The summary table will be displayed by PT only.

All SAEs will be tabulated based on the number and percentage of participants who experienced the event. Separate summaries will also be provided for study intervention-related SAEs. The summary tables will be displayed by PT.

A study intervention-related SAE is defined as an SAE for which the investigator classifies the relationship to study intervention as “Yes”. A worst-case scenario approach will be taken to handle missing data, *i.e.* the summary table will include events with the relationship to study intervention as ‘Yes’ or missing.

Unadjusted Relative risks with Wald confidence intervals based on observed frequencies, for the proportions of participants with common ($\geq 5\%$ in either treatment group) AEs will be calculated for otilimab versus placebo.

Relative risks will not be calculated if there are no events in either of the two treatment arms being compared. The relative risks and exact confidence interval will be plotted on log base 10 scale.

The adverse events with calculated relative risks will be presented in decreasing order as per the IDSL standard.

5.5.2.1. Adverse Events of Special Interest

The following will be considered adverse events of special interest (AESI) for the purpose of analyses:

- Cytokine release syndrome (CRS)
- Serious hypersensitivity reactions
Note: these will be adjudicated by the SRT.
- Infusion site reactions
- Neutropenia \geq Grade 3 ($<1.0 \times 10^9/L$)
- Serious infections

Listings of event characteristics will be provided for each AESI respectively. For AESIs with more than 8 events a summary of event characteristics will be provided for each AESI respectively, including number and percentage of participants with any event, number and percentage of events, maximum intensity, outcomes and the action taken for the event. The worst-case approach will be applied at participant level for the maximum intensity, *i.e.* a participant will only be counted once as the worst case from all the events experienced by the participant.

5.5.3. Additional Safety Assessments

5.5.3.1. Laboratory Data

Summaries of worst-case grade increase from baseline grade will be provided for all the lab tests that are gradable by a modified CTCAE v5. These summaries will display the number and percentage of participants with a maximum post-baseline grade increasing from their baseline grade. Any increase in grade from baseline will be summarized along with any increase to a maximum grade of 3 and any increase to a maximum grade of 4. Missing baseline grade will be assumed as grade 0. For laboratory tests that are graded for both low and high values, summaries will be done separately and labelled by direction, *e.g.*, sodium will be summarized as hyponatremia and hypernatremia separately.

The CTCAE v5 grades were modified to remove grading criteria that cannot be derived programmatically with the data collected (see footnotes). The modified CTCAE v5 grades are defined as follows:

Laboratory parameters of interest ¹	Grade			
	1	2	3	4
HEMOGLOBIN decreased (CTCAE term is Anemia) ²	<LLN - 10.0 g/dL; <LLN - 6.2 mmol/L; <LLN - 100 g/L	<10.0 - 8.0 g/dL; <6.2 - 4.9 mmol/L; <100 - 80 g/L	<8.0 g/dL; <4.9 mmol/L; <80 g/L	-
HEMOGLOBIN increased	>0 - 2 g/dL	>2 - 4 g/dL	>4 g/dL	-
LEUKOCYTE (White blood cell) decreased	<LLN - 3000/mm ³ ; <LLN - 3.0 x 10 ⁹ /L	<3000-2000/mm ³ ; <3.0 - 2.0 x 10 ⁹ /L	<2000-1000/mm ³ ; <2.0 - 1.0 x 10 ⁹ /L	<1000/mm ³ ; <1.0 x 10 ⁹ /L
LYMPHOCYTE COUNT decreased	<LLN - 800 /mm ³ ; <LLN - 0.8 x 10 ⁹ /L	<800 - 500 /mm ³ ; <0.8 - 0.5 x 10 ⁹ /L	<500 - 200 /mm ³ ; <0.5 - 0.2 x 10 ⁹ /L	<200/mm ³ ; <0.2 x 10 ⁹ /L
LYMPHOCYTE COUNT increased	-	>4,000 - 20,000 /mm ³ ; >4 - 20 x 10 ⁹ /L	>20,000 /mm ³ ; >20 x 10 ⁹ /L	-
NEUTROPHIL COUNT decreased	<LLN - 1,500 /mm ³ ; <LLN - 1.5 x 10 ⁹ /L	<1,500 - 1,000 /mm ³ ; <1.5 - 1.0 x 10 ⁹ /L	<1,000 - 500 /mm ³ ; <1.0 - 0.5 x 10 ⁹ /L	<500 /mm ³ ; <0.5 x 10 ⁹ /L
PLATELET COUNT decreased	<LLN - 75,000 /mm ³ ; <LLN - 75.0 x 10 ⁹ /L	<75,000 - 50,000 /mm ³ ; <75.0 - 50.0 x 10 ⁹ /L	<50,000 - 25,000 /mm ³ ; <50.0 - 25.0 x 10 ⁹ /L	<25,000 /mm ³ ; <25.0 x 10 ⁹ /L
AST (SGOT)	>ULN - 3.0 x ULN if baseline was normal; 1.5 - 3.0 x baseline if baseline was abnormal	>3.0 - 5.0 x ULN if baseline was normal; >3.0 - 5.0 x baseline if baseline was abnormal	>5.0 - 20.0 x ULN if baseline was normal; >5.0 - 20.0 x baseline if baseline was abnormal	>20.0 x ULN if baseline was normal; >20.0 x baseline if baseline was abnormal
ALP	>ULN - 2.5 x ULN if baseline was normal; 2.0 - 2.5 x baseline if baseline was abnormal	>2.5 - 5.0 x ULN if baseline was normal; >2.5 - 5.0 x baseline if baseline was abnormal	>5.0 - 20.0 x ULN if baseline was normal; >5.0 - 20.0 x baseline if baseline was abnormal	>20.0 x ULN if baseline was normal; >20.0 x baseline if baseline was abnormal

Laboratory parameters of interest ¹	Grade			
	1	2	3	4
ALT (SGPT)	>ULN - 3.0 x ULN if baseline was normal; 1.5 - 3.0 x baseline if baseline was abnormal	>3.0 - 5.0 x ULN if baseline was normal; >3.0 - 5.0 x baseline if baseline was abnormal	>5.0 - 20.0 x ULN if baseline was normal; >5.0 - 20.0 x baseline if baseline was abnormal	>20.0 x ULN if baseline was normal; >20.0 x baseline if baseline was abnormal
BLOOD BILIRUBIN increased	>ULN - 1.5 x ULN if baseline was normal; > 1.0 - 1.5 x baseline if baseline was abnormal	>1.5 - 3.0 x ULN if baseline was normal; >1.5 - 3.0 x baseline if baseline was abnormal	>3.0 - 10.0 x ULN if baseline was normal; >3.0 - 10.0 x baseline if baseline was abnormal	>10.0 x ULN if baseline was normal; >10.0 x baseline if baseline was abnormal
ALBUMIN (Hypo-albuminemia)	<LLN - 3 g/dL; <LLN - 30 g/L	<3 - 2 g/dL; <30 - 20 g/L	<2 g/dL; <20 g/L	-
APTT Activated partial thromboplastin time prolonged	>ULN - 1.5 x ULN	>1.5 - 2.5 x ULN	>2.5 x ULN	-
CALCIUM (Hypercalcemia)	Corrected serum calcium of >ULN - 11.5 mg/dL; >ULN - 2.9 mmol/L; Ionized calcium >ULN - 1.5 mmol/L	Corrected serum calcium of >11.5 - 12.5 mg/dL; >2.9 - 3.1 mmol/L; Ionized calcium >1.5 - 1.6 mmol/L	Corrected serum calcium of >12.5 - 13.5 mg/dL; >3.1 - 3.4 mmol/L; Ionized calcium >1.6 - 1.8 mmol/L	Corrected serum calcium of >13.5 mg/dL; >3.4 mmol/L; Ionized calcium >1.8 mmol/L
CALCIUM (Hypocalcemia)	Corrected serum calcium of <LLN - 8.0 mg/dL; <LLN - 2.0 mmol/L; Ionized calcium <LLN - 1.0 mmol/L	Corrected serum calcium of <8.0 - 7.0 mg/dL; <2.0 - 1.75 mmol/L; Ionized calcium <1.0 - 0.9 mmol/L	Corrected serum calcium of <7.0 - 6.0 mg/dL; <1.75 - 1.5 mmol/L; Ionized calcium <0.9 - 0.8 mmol/L	Corrected serum calcium of <6.0 mg/dL; <1.5 mmol/L; Ionized calcium <0.8 mmol/L
CPK increased	>ULN - 2.5 x ULN	>2.5 x ULN - 5 x ULN	>5 x ULN - 10 x ULN	>10 x ULN
CREATININE increased	>ULN - 1.5 x ULN	>1.5 - 3.0 x baseline; >1.5 - 3.0 x ULN	>3.0 x baseline; >3.0 - 6.0 x ULN	>6.0 x ULN

Laboratory parameters of interest ¹	Grade			
	1	2	3	4
GGT increased	>ULN - 2.5 x ULN if baseline was normal; 2.0 - 2.5 x baseline if baseline was abnormal	>2.5 - 5.0 x ULN if baseline was normal; >2.5 - 5.0 x baseline if baseline was abnormal	>5.0 - 20.0 x ULN if baseline was normal; >5.0 - 20.0 x baseline if baseline was abnormal	>20.0 x ULN if baseline was normal; >20.0 x baseline if baseline was abnormal
GLUCOSE (Hypoglycemia)	<LLN - 55 mg/dL; <LLN - 3.0 mmol/L	<55 - 40 mg/dL; <3.0 - 2.2 mmol/L	<40 - 30 mg/dL; <2.2 - 1.7 mmol/L	<30 mg/dL; <1.7 mmol/L
LDH (Blood lactate dehydrogenase increased)	>ULN	-	-	-
POTASSIUM (Hyperkalemia)	>ULN – 5.5 mmol/L	>5.5 – 6.0 mmol/L;	>6.0 – 7.0 mmol/L	>7.0 mmol/L
POTASSIUM (Hypokalemia) ₃	<LLN – 3.0 mmol/L		<3.0 – 2.5 mmol/L	<2.5 mmol/L
SODIUM (Hypernatremia)	>ULN – 150 mmol/L	>150 - 155 mmol/L	>155 - 160 mmol/L	>160 mmol/L
SODIUM (Hyponatremia) ⁴	<LLN - 130 mmol/L	-	120-129 mmol/L	<120 mmol/L
INR increased ⁵	>1.2 – 1.5	>1.5 – 2.5	>2.5	-
Eosinophils ⁶	>ULN and >Baseline	-	-	-

1. Removal of cardiac troponin I or T increased gradings. Specifically Grade 1 indicated by levels above the upper limit of normal and below the level of myocardial infarction as defined by the manufacturer and Grade 3 indicated by levels consistent with myocardial infarction as defined by the manufacturer
2. Removal of Grade 3 defined as transfusion indicated by transfusion and grade 4 indicated by Life-threatening consequences or urgent intervention indicated
3. Removal of Grade 2 defined as symptomatic with $< \text{LLL} - 3.0 \text{ mmol/L}$
4. Removal of Grade 2 defined as 125-129 mmol/L and asymptomatic, Grade 3 is re-defined as 120-129 mmol/L i.e. conservatively including the grade 2 criteria of "125-129 mmol/L and asymptomatic" into the Grade 3 criteria of "120-124 mmol/L regardless of symptoms; 125-129 mmol/L symptomatic" as asymptomatic/symptomatic is not collected.
5. Removal of Grade 1 indicated by $>1 - 1.5 \times$ baseline if on anticoagulation; Grade 2 indicated by $>1.5 - 2.5 \times$ baseline if on anticoagulation; and Grade 3 indicated by $>2.5 \times$ baseline if on anticoagulation.
6. Removal of Grade 3 defined as steroids initiated

Note: The grading will be rederived for any laboratory parameters with modifications from the CTCAE V5

For lab tests that are not gradable by modified CTCAE v5, summaries of worst-case changes from baseline with respect to normal range will be generated. Decreases to low, changes to normal or no changes from baseline, and increases to high will be summarized for the worst-case post-baseline. If a participant has a decrease to low and an increase to high during the same time interval, then the participant is counted in both the "Decrease to Low" categories and the "Increase to High" categories.

Separate summary tables for haematology, and chemistry laboratory tests will be produced. Liver function laboratory tests will be included with chemistry lab tests.

In addition, if any AE of CRS symptoms is reported a summary table of hematology, CRP, D-dimer and ferritin will be produced.

Summaries of hepatobiliary laboratory events will be provided in addition to what has been described above. Possible Hy's law cases defined as any elevated alanine aminotransferase (ALT) $\geq 3 \times$ upper limit of normal (ULN) and total bilirubin $\geq 2 \times$ ULN ($>35\%$ direct bilirubin) or ALT $\geq 3 \times$ ULN and INR > 1.5 will be presented in a plot of maximum ALT vs maximum total bilirubin.

5.5.3.2. Vital Signs

Summaries of worst-case systolic blood pressure (SBP), diastolic blood pressure (DBP) and heart rate relative to Potential Clinical Importance (PCI) post-baseline relative to baseline will be provided. This will include all post-baseline assessments.

Potential Clinical Importance ranges are defined as follows:

Vital Sign Parameter	Units	Clinical Concern Range	
		Lower	Upper
Absolute			
Systolic blood pressure	mmHg	<80	>170
Diastolic blood pressure	mmHg	<45	>110
Heart Rate	bpm	<40	>100
Change from Baseline			
Systolic blood pressure	mmHg	≥30↓	≥30↑
Diastolic blood pressure	mmHg	≥20↓	≥20↑

Worst case summaries will display the number and percentage of participants with changes in the absolute values “To Low”, “To w/in Range or No Change” or “To High” post baseline relative to baseline. Participants will be reported in both the “To Low” and “To High” categories if both of these changes are observed post-baseline. Participants will only be reported in the “To w/in Range or No Change” category if they experience no “To Low” or “To High” changes post-baseline. The summaries will also display the number and percentage of participants with “PCI Increase from Baseline”, “PCI Decrease from Baseline” or “No PCI Change from Baseline”. Participants will be reported in the “PCI Increase from Baseline” (“PCI Increase from Baseline”) categories if the upper (/lower) change from baseline clinical concern range value is observed, respectively. Participants will be reported in both the “PCI Increase from Baseline” and “PCI Decrease from Baseline” categories if both of these changes are observed post-baseline. Participants will only be reported in the “No PCI Change from Baseline” category if they experience no “PCI Increase from Baseline” or “PCI Decrease from Baseline” changes post-baseline.

In addition, summaries of change from baseline in systolic blood pressure (SBP), diastolic blood pressure (DBP), respiratory rate and temperature over Days 1 to 28 will be provided.

5.5.3.3. ECG

A summary of the number and percentage of participants with ECG findings will be summarized by treatment. The ECG findings to be summarized are the ECG interpretation and clinical significance of abnormal ECGs. Participants with missing baseline values will be excluded from this summary.

5.6. Other Analyses

5.6.1. Pharmacokinetics (PK)

Pharmacokinetic concentrations will be listed and summarised by visit.

5.6.2. Population Pharmacokinetics

Sparse PK samples will be analysed using population PK approach. Otilimab PK data from this study will be combined with PK data after IV administration from 4 studies in

healthy volunteers, RA and MS adult participants. The PK parameters reported will be clearance, steady-state volume of distribution and AUC.

Further details will be provided in a supplemental analyses plan.

5.6.3. Pharmacodynamics

Pharmacodynamic biomarkers measures including free GM-CSF, key markers of inflammation including, but not limited to CRP, serum ferritin and inflammatory cytokines as appropriate will be listed and summarised by visit.

Further details will be provided in a supplemental analyses plan.

5.6.4. Pharmacokinetics/Pharmacodynamics

Exposure-response relationship for key efficacy, safety and PD endpoints will be explored graphically and if data permits (range of otilimab concentrations observed in this study is wide enough) will be followed by model-based analysis.

Further details will be provided in a supplemental analyses plan.

5.7. Interim Analyses

Details of the interim analyses and required outputs are provided in the IDMC Charter and IDMC Statistical Analyses Plan.

6. SUPPORTING DOCUMENTATION

6.1. Appendix 1 Abbreviations and Trademarks

6.1.1. List of Abbreviations

Abbreviation	Description
AE	Adverse Event
AESI	Adverse Event of Special Interest
ANCOVA	Analyses of Covariance
AUC	Area Under the Curve
BIPAP	Bilevel Positive Airway Pressure
CL	Clearance
COVID-19	Corona Virus Disease 2019
CPAP	Continuous Positive Airway Pressure
CRP	C-Reactive Protein
CRS	Cytokine Release Syndrome
CTCAE	Common Terminology Criteria for Adverse Events
DBP	Diastolic Blood Pressure
ECG	Electrocardiogram
eCRF	Electronic Case Record Form
FCS	Fully Conditional Specification
FiO ₂	Concentration of Inspired Oxygen
FU	Follow-up
GM-CSF	Granulocyte-macrophage colony-stimulating factor
GSK	GlaxoSmithKline
ICH	International Conference on Harmonization
ICU	Intensive Care Unit
IDMC	Independent Data Monitoring Committee
IDSL	Integrated Data Standards Library
IND	Investigational New Drug
IRT	Interactive Response Technology
IV	Intravenous
MAR	Missing at random
MCMC	Markov Chain Monte Carlo
MI	Multiple imputation
MITT	Modified Intent-To-Treat
MS	Multiple Sclerosis
OPS	Output and Programming Specification
PCI	Potential Clinical Importance
PD	Pharmacodynamic
PK	Pharmacokinetic
PT	Preferred Term
RA	Rheumatoid Arthritis
RMST	Restricted Mean Survival Time
SAE	Serious Adverse Event

Abbreviation	Description
SAP	Statistical Analysis Plan
SBP	Systolic Blood Pressure
SDTM	Study Data Tabulation Model
SOC	System Organ Class
SOFA	Sequential Organ Failure Assessment
SpO ₂	Blood Oxygen Saturation
SRT	Safety Review Team
ULN	Upper Limit of Normal
WHO	World Health Organisation

6.1.2. Trademarks

Trademarks of the GlaxoSmithKline Group of Companies
None

Trademarks not owned by the GlaxoSmithKline Group of Companies
None

6.2. Appendix 2: Changes to Protocol-Planned Analyses

Changes to protocol-planned analyses include:

- The number of interim analyses in the group sequential design has been reduced to three interims for futility and one for efficacy. This is due to recruitment being completed prior to formal interim analyses number 4 (on approximately 600 participants), hence it was decided to remove this formal analysis on approximately 600 participants and continue to the final analyses only. The final analyses boundary has been adjusted to carry over the alpha that would have been spent on the 600-participant analysis. The hierarchy has been updated accordingly but previous boundaries were not amended.
- The study design has been updated such that the final analyses on the primary endpoint will be conducted once all participants have been randomised and completed to Day 28 or withdrawn.
- The proposed hierarchy for testing secondary endpoints, refer to Section 2 for full details.
- Updates to secondary endpoint related to hospital discharge, refer to Section 5.3.1.9 and Section 5.3.1.10 for full details.
- For exploratory endpoints on improvement in SOFA, Blood Oxygen Saturation (SpO₂), Concentration of Inspired Oxygen (FiO₂) and SpO₂/FiO₂ ratio, the endpoints have been clarified to include recovery as part of composite strategy.
- The exploratory endpoint “Time to Improvement of at Least 2 Categories Relative to Baseline on an Ordinal Scale up to Day 60” has been updated to “Time to Improvement of at Least 2 Categories Relative to Baseline in Clinical Status up to Day 60” for consistency over the use of clinical status rather than ordinal scale.

6.3. Appendix 3: Statistical Modelling

6.3.1. Multiple Imputation

Multiple imputation will be utilized to impute data that is missing following withdrawal of the participant from the study. Each data type will use one set of imputations with all endpoints that depend on that data type being derived from the intermediate dataset.

The statistical model used for the multiple imputation data generation will use one of two approaches depending on data type:

- Continuous endpoints will use the Markov Chain Monte Carlo (MCMC) method with adjustment for covariates.
- Binary and ordinal endpoints will use a two-stage approach:
 1. First intermittent missing data will be imputed using MCMC followed by adaptive rounding [Carpenter, 2012] step to create a monotone structure.
 2. Second a monotone logistic regression imputation will be performed to impute data post-study withdrawal, this model will include the analyses covariates. If logistic regression step fails to converge the following back-up options including:
 - i. A discriminant function [Brand, 1999] may be used in place of logistic.
 - ii. MCMC with adaptive rounding.

A sufficient number of imputations will be performed to ensure the stability of the estimates, the current plan is 10,000 imputation. The results of analysis from each complete imputed dataset will be combined using Rubin's rule. Table 7 details the models, covariates and the seed to be used for the analyses.

For subgroup analyses the multiple imputation model will be identical to the main endpoint analyses and the interaction term will be added into the analysis step. The chi-squared test statistic of the interaction term will be pooled using the procedure of Rubin (1987) and Li (1991).

Table 7 Multiple Imputation Specifications

Endpoint	Model	Covariates	Post Baseline Timepoints Included in Prediction Model	Initial Seed
Participants alive and free of respiratory failure at Day 7, 14, 28, 42, and 60.	Monotone Binary Logistic Regression	Treatment, Clinical Status at Baseline, Age Group at Baseline	Days 7,14,28,42 and 60	3764
All-cause mortality at Day 60.	Monotone Binary Logistic Regression	Treatment, Clinical Status at Baseline, Age Group at Baseline	Days 7,14,28,42 and 60	1734
Participants alive and independent of supplementary oxygen at Day 7, 14, 28, 42, and 60	Monotone Binary Logistic Regression	Treatment, Clinical Status at Baseline, Age Group at Baseline	Days 7,14,28,42 and 60	9849
Admission to ICU up to Day 28	Monotone Binary Logistic Regression	Treatment, Clinical Status at Baseline, Age Group at Baseline	Days 4, 7, 10, 14 and 28	6935
If the number of participants is small within a category of a covariate, then the covariate categories may be refined. If the category cannot be refined further, then the covariate may be included as a continuous measure.				

The seeds were generated using the following code:

DATA seeds;

DO i=1 to 4;

seed=int(10000*ranuni(214094));

OUTPUT;

END;

RUN;

If additional seeds are required, then the initial seed as specified will be incremented by 1.

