6.2. Appendix 2: Statistical Modelling

6.2.1. Multiple Imputation

Multiple imputation will be utilized to impute data that is missing following intercurrent events as detailed in the endpoint derivations.

For endpoints that are derived from the clinical status ordinal scale, as shown below, missing data will first be imputed on the ordinal scale prior to deriving the binary endpoints:

- All-cause Mortality
- Alive and Free of Respiratory Failure
- Alive and Independent of Supplementary Oxygen

For other endpoints, missing data will be imputed directly on the binary endpoint.

A monotone logistic regression imputation will be performed on both binary and ordinal endpoints adjusting for treatment and the analyses covariates.

This will be performed in a stepwise fashion, where each visit will be imputed from the selected visits preceding it, such that intermediate missing data (data that is between two non-missing values) will be imputed based only on the data that precedes it.

Death will always be considered a permanent event, such that if a subject is imputed to have died, missing data succeeding it will always be assigned the state of 'died'.

As it is expected that the data may have either a complete separation pattern or a quasi-complete separation pattern, observations will be added to each response group and then this augmented data will be used to fit a weighted logistic regression as proposed by [White \(2010\)](#)

If the logistic regression step fails to converge despite augmenting the likelihood, then a discriminant function [[Brand, 1999](#)] may be used in place of the logistic function.

A sufficient number of imputations will be performed to ensure the stability of the estimates, 10,000 imputation will be used. The results of analysis from each complete imputed dataset will be combined using Rubin's rule. [Table 4](#) details the models, covariates and the seed to be used for the analyses.

For subgroup analyses the multiple imputation model will be identical to the main endpoint analyses and the interaction term will be added into the analysis step. The chi-squared test statistic of the interaction term will be pooled using the procedure of [Rubin \(1987\)](#) and [Li \(1991\)](#).

Table 4 Multiple Imputation Specifications

Endpoint	Covariates	Post-Baseline Timepoints Included in Prediction Model	Initial Seed

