5.2. Primary Endpoint(s) Analyses

5.2.1. Definition of Endpoint(s)

Participants are free of respiratory failure if they are in category 1, 2, 3 or 4 from the GlaxoSmithKline (GSK) modified ordinal scale adapted from World Health Organization (WHO) scale 2020 (See [Table 4](#) - Clinical Status using Ordinal Scale).

Participants will meet the endpoint if they are alive and free of respiratory failure at Day 28. As participants may be discharged from the investigator site prior to Day 28, analysis windows will be used to define the endpoint, further details on analysis windows will be provided in the Output and Programming Specification (OPS).

Table 4 Clinical Status using Ordinal Scale**Ordinal Scale (GSK modified version, adapted from WHO, 2020 version)**

CCI - This section contained Clinical Outcome Assessment data collection questionnaires or indices, which are protected by third party copyright laws and therefore have been excluded.

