6.3.1.1. Adaptive Rounding

The adaptive rounding algorithm [Carpenter, 2012] is:

1. For binary variable j in imputed dataset $k = 1, \dots, K$, let $\bar{Y}_{j,k}$ denote the mean of the observed (binary) and imputed (continuous) values.
2. Construct the threshold $c_{j,k} = \bar{Y}_{j,k} - \Phi^{-1}(\bar{Y}_{j,k}) \sqrt{\bar{Y}_{j,k}(1 - \bar{Y}_{j,k})}$
3. In imputed data set k , re-code continuous imputed values of the binary variable Y_j according to the following rule: $Y_{i,j} \leq c_{j,k}$ becomes $Y_{i,j} = 0$, and $Y_{i,j} > c_{j,k}$ becomes $Y_{i,j} = 1$.

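### Part 1 SAP 6.3.1 asks for one set of imputations per data type, but Table 7 imputes three overlapping clinical-status endpoints separately, and its Day 60 mortality model appears to omit the last observed clinical category.

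*SAP*

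**What the plan says.** The opening paragraph of Part 1 SAP 6.3.1 states: "Each data type will use one set of imputations with all endpoints that depend on that data type being derived from the intermediate dataset".

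Table 7, in the same section, has four rows. Three concern the participant's clinical state:

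- alive and free of respiratory failure at Days 7 to 60, seed 3764;
- all-cause mortality at Day 60, seed 1734;
- alive and independent of supplementary oxygen at Days 7 to 60, seed 9849.

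The fourth row is ICU admission, seed 6935. Every row specifies "Monotone Binary Logistic Regression" with covariates "Treatment, Clinical Status at Baseline, Age Group at Baseline". The three clinical-state rows list "Days 7,14,28,42 and 60" as post-baseline timepoints in the prediction model. The table does not say which variable is used at those days.

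The endpoints overlap by definition. Section 5.2.1 says: "Participants are free of respiratory failure if they are in category 1, 2, 3 or 4 from the GlaxoSmithKline (GSK) modified ordinal scale". Section 5.3.1.5 takes categories 1 to 3 for oxygen independence. Both require the participant to be alive.

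Part 2 SAP 6.2.1 does it differently. For these same endpoints, "missing data will first be imputed on the ordinal scale prior to deriving the binary endpoints", with one seed (122) and imputed death treated as permanent.

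**The concern.** A programmer cannot apply the one-set rule and also run three separately seeded binary imputations of overlapping endpoints. Part 1 contains no text that links the draws or carries an imputed death from one endpoint to another.

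The more substantive problem is the mortality row. Everyone who needs a Day 60 imputation was alive at the last visit. If the post-baseline predictor is the row's own outcome, their histories are all the same: not dead. Within a given arm, baseline category and age group, a participant last seen at home and one last seen ventilated then get the same imputed risk of death. Protocol 8.4.2 expects most missing data to be loss after discharge, so loss is related to the clinical state that this model leaves out.

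Day 60 mortality is in the Part 1 testing hierarchy (Part 1 SAP 5.3.3.1), so the plan should say clearly how it is imputed.

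**Working it through.** **1. The plan's own figures.** The printed code starts from "seed=int(10000*ranuni(214094" and loops four times. Run as a multiplicative generator (modulus 2^31-1, multiplier 397204094; these constants are not in the documents), it returns 3764, 1734, 9849 and 6935. These are exactly the Table 7 seeds. The same generator returns 122 for Part 2. The Part 1 table is thus set up for four separate runs, one per row.

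**2. Text against table.** The sentences after the rule use data type for continuous versus binary and ordinal. Whether it means that, or means the clinical scale, free of failure, oxygen independence and mortality fall under one type. The text then requires one run, while Table 7 specifies three.

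**3. Imputed risk of death by Day 60.** The documents give no transition or loss rates, so both illustrations below use assumed ones. The separate-row risk is P(dead by Day 60 | alive at last visit). The status-based risk is P(dead by Day 60 | last observed category).

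*Illustration A*: a four-state chain at Days 7, 14, 28, 42 and 60, with assumed 55% alive and free at Day 28, 29% dead by Day 28 and 34% dead by Day 60.

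| Last seen | Status-based | Separate row | Gap (points) |
|---|---|---|---|
| Home, Day 14 | 2.4% | 17.9% | +15.5 |
| Home, Day 28 | 1.1% | 7.9% | +6.8 |
| Respiratory failure, Day 28 | 28% | 7.9% | -20.1 |

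*Illustration B*: states are category 1-3, 4, 5, 6-7 and dead. The start is 60% category 5 and 40% category 6. Visit-to-visit rows are (.97, .02, .005, 0, .005), (.60, .30, .06, .02, .02), (.22, .25, .30, .13, .10) and (.06, .10, .14, .48, .22). The death column is multiplied by 0.6, 1 or 1.6 and each row rescaled to sum to 1. Day 60 mortality is then 23.8%, 34.2% or 45.2%. For a participant last seen in category 1-3:

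- Day 14: separate row 9.7-18.2%, status-based 1.0-2.7%.
- Day 28: separate row 5.3-9.6%, status-based 0.6-1.7%.

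Table 7 does adjust for baseline category. Starting chain B (multiplier 1) entirely in category 5 gives 10.3% against 1.7% for Day 14. Starting entirely in category 6 gives 20.7% against 1.7%. Adjustment changes the size of the gap but does not close it.

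**4. Effect on one arm.** Shift = share lost × gap, with 3-5% lost from home (assumed).

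- Day 14 gap: 0.03 × 15.5 = 0.5 and 0.05 × 15.5 = 0.8 points.
- Day 28 gap: 0.03 × 6.8 = 0.2 and 0.05 × 6.8 = 0.3 points.
- Chain B extremes: 0.03 × (5.3 - 0.6) = 0.1 and 0.05 × (18.2 - 2.7) = 0.8 points.

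Unequal loss of 2% against 6% would create a between-arm difference of 0.04 × 15.5 = 0.6 points (Day 14 gap) or 0.04 × 6.8 = 0.3 points (Day 28 gap).

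**5. Scale.** With 400 per arm and 34% mortality, the standard error of the difference is √(2 × 0.34 × 0.66 / 400) = 0.0335, about 3.3 points. A 0.6-point artefact is about 0.2 standard errors.

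**6. Contradictory records.** A simulation of 800 participants used a chain of this kind, with 2% or 5% loss per visit after discharge (13-56 lost) and separate draws. In it, 4-12% of lost-participant imputations were both dead and free of respiratory failure at Day 60. A further 1-4% were off oxygen but not free of respiratory failure. With one ordinal imputation both rates are zero by construction.

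**The case against.** The case on the other side is substantial.

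- *Data type is undefined*, so Table 7 might be read as one run per row, with that row's visits derived from it. This strains the text, which uses the term for continuous versus binary and ordinal data.
- *The predictor is unnamed.* The Output and Programming Specification, which is not among the documents, may supply it. This stands: the mortality point depends on the natural reading. A reader might infer that imputed deaths ignore everything known about the participant. They do not; baseline status, age group, arm and survival to earlier visits are used.
- *The tipping-point analysis* (Part 1 SAP 5.2.3.1, applied to Day 60 mortality by 5.3.3.1) varies the assumed rate among missing participants from 0 to 1, independently by arm. It covers any over-imputation described here, but does not correct the main estimate. Time to all-cause mortality censors at withdrawal and does not use this imputation.
- *No planned test combines the three imputed variables.* A reader might infer that contradictory records invalidate the tests or bias the primary endpoint. The documents do not support that. Each endpoint has its own model, and each row alone can be a valid missing-at-random analysis given the variables it contains.
- *The rates are assumed*, and Protocol 8.4.2 expects missing data to be minimal. This stands.
- *Adaptive rounding* is prescribed for binary and ordinal endpoints, yet its algorithm begins "For binary variable j in imputed dataset" and cannot be applied to a mean above 1. A reader might take this for a working failure. No Table 7 row is ordinal, so it is leftover wording.
- *The Part 2 method does not transfer unchanged.* It imputes intermittent gaps from preceding data only, so it could place a death before a visit at which the participant was observed alive. This stands and shapes the fix.

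**Conclusion.** The conflict between the text of Part 1 SAP 6.3.1 and Table 7 is on the page and should be resolved. On the natural reading of Table 7, imputations are unlinked across endpoints. The Day 60 mortality model then over-imputes death for participants lost after discharge and under-imputes it for those lost in respiratory failure.

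The likely effect is small: about 0.2-0.8 points on an arm's Day 60 mortality, well inside the 3.3-point standard error of the difference. That size rests on assumed transition rates, 3-5% loss from home and an unnamed predictor. The finding is incoherence across endpoints and a weaker model than the sponsor already uses in Part 2. It is not evidence that the primary result is wrong.

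**What to change.** For the final Part 1 analysis:

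- Replace the first three rows of Table 7 with one imputation of ordinal clinical status: one seed, death permanent, and the augmented logistic fit of Part 2 SAP 6.2.1. Derive free of respiratory failure, oxygen independence and mortality from it.
- Add a rule that death is never imputed at a visit before one at which the participant is observed alive.
- If the Day 28 primary result has already been produced under Table 7, as Protocol 8.4.2 suggests, keep it. State which of the two instructions was followed, and report the re-imputed result as a sensitivity analysis.
- As a minor clean-up, confine the adaptive-rounding step to binary variables.

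The cost is some extra programming, mostly reuse of the Part 2 method, and a documented departure from Table 7. No new data are needed.
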